11. Was the rTMS treatment completed? No Yes
12. If No, specify the primary reason using the codes (see last page for codes) _____
13. rTMS administrator's initials: _____

CODES:

1 = Equipment malfunction	4 = Adverse Device Event/Adverse Event
2 = Participant refused	5 = Unanticipated Adverse Device Event/Serious Adverse Event
3 = Staff error	6 = Other, specify _____

VA COOPERATIVE STUDY #556
The Effectiveness of rTMS in Depressed VA Patients

Site ____ Participant # _____ Alpha Code _____ Date ___/___/___- MM / DD / YYYY

Form 20 – HRSD and MADRS

Circle Visit Below:

Screening

Acute Treatment Phase Sessions: 5 10 15 20 25 30

Follow-up Phase Weeks: 4 8 12 16 20 24

Interviewer's Initials:	_____		
Start Time:	_____ (24 hour clock)		
MANUAL SCORING INSTRUCTIONS: Write the score of the item in the box for the 24 HRSD items. Take the sum of these values and write it in the Total HRSD Score box at the end of the form.			
Introductory Questions: "I'd like to ask you some questions about the past week. Since last (DAY OF THE WEEK), how have you been feeling? Have you noticed any change in how you have been feeling during the past week compared to before?"			
Interview Guide	HRSD Scoring Criteria	MADRS Scoring Criteria	
SLEEP (Early and Middle Insomnia)			
"Let's talk about your sleep. During the past week, what were your usual hours of going to sleep and waking up? How many hours of sleep at night would be best for you?" If patient had a significant period of euthymia in past 5 years: "How many hours of sleep did you get when you were not depressed and feeling well?"			
"Have you had any trouble this week falling asleep at the beginning of the night?" After you have gone to bed, how long has it been taking you to fall asleep? How many nights this week have you had trouble falling asleep?	H4. INSOMNIA – EARLY  (0) Less than or equal to 1/2 hr to fall asleep (always add a point for use of a hypnotic at bedtime)  (1) Greater than 1/2 hr at least 2 days and less than 5 nights in the past week  (2) Greater than 1/2 hr 5 or more nights in the past week		

Interview Guide	HRSD Scoring Criteria	MADRS Scoring Criteria

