APPENDIX M

HEALTH ECONOMICS AND COST ANALYSIS

A. Overview

The proposed project will compare the effectiveness of rTMS to that of sham-rTMS among patients with treatment-resistant major depression participating in CSP 556. The economic analysis will comprise three parts: (1) cost-identification analysis to document the cost of the intervention; (2) a cost-consequences analysis to estimate its impact in both short- and long-term time horizons (i.e., 24-weeks post-treatment, and 4- to 12-months post-treatment, respectively); and (3) a cost-effectiveness analysis for rTMS therapy. The intervention cost-identification analysis will document the expected cost of the intervention to the VA in a typical site. The cost-consequences analysis will compare the difference in average total and average variable costs of care during a one-year period between rTMS therapy and usual outpatient depression care for treatment-resistant patients. The cost-effectiveness analysis will calculate the average incremental treatment cost per incremental depression remission for these same participants and time period. Remission is defined as a Hamilton depression score less than 10.

An economic analysis is central to CSP 556, because any future plan to implement rTMS technology within VHA will require estimates of the expected investment cost for new equipment, staff time, and other resources and because any decision to invest substantial new resources into rTMS therapy may depend on its expected effects on services utilization, cost, and patients' health status balanced against that investment.

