It cannot be known *a priori* if rTMS therapy will increase or reduce usual VA health care costs associated with treatment-resistant depression. This innovation, rTMS, may increase costs during the acute treatment phase due to more frequent contact with outpatient providers, greater frequency of lab tests, use of an expensive rTMS medical device, and greater use of other resources. However, these extra costs could be partially or completely offset by savings from reduced likelihood of later hospitalization, reduced likelihood of receiving electroconvulsive therapy (ECT), reduced use of psychotropic medications, and/or reduced frequency of depression-related medical encounters. If rTMS therapy increases the likelihood of a full remission and/or reduces the likelihood of a recurrence, cost-offset effects will tend to accumulate over time. Because there is presently little evidence on the cost and effectiveness of rTMS in usual clinical settings, the magnitude of shorter and longer term potential cost differences between rTMS and usual care are unknown. Two hypotheses about the short-term (24-weeks post-treatment) and longer term (6- to 12-months post-treatment) cost consequences of rTMS therapy will therefore be tested:

1. Relative to usual care, total direct and indirect VA costs related to rTMS therapy for treatment-resistant depression will be less than total costs associated with usual care at 6-weeks post-treatment.
2. Relative to usual care, total direct and indirect VA costs related to rTMS therapy for treatment-resistant depression will be less than total costs associated with usual care at 6- to 12-months post-treatment.

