The short-term 24-week period was chosen to coincide with the collection of clinical endpoints at the end of the CSP 556 follow-up phase. The longer term 6- to 12-month period was chosen to maximize the opportunity to observe cost offsets from rTMS. The reason for specifying 6- to 12-months rather than a single time period is that due to extant data lags we do not know in advance how long of a retrospective period will be available to us, given the potential variability in the timing of patient recruitment. Maximization of sample size is paramount to accurate cost estimation. Therefore, we will select the longest 6- to 12-month post-treatment period that will allow us to include the largest sample of study participants. We believe that nearly all patients will have completed treatment and will have 6-months post-treatment cost data available before the end of the three-year study. A longer cost consequence follow-up will be pursued, if the extant data are available. Cost consequences

results will be discussed in terms of statistical significance and the magnitude and types of differences (e.g., inpatient and outpatient).

We will then estimate the cost-effectiveness of rTMS therapy in producing a sustained remission from depression (HRSD \leq 10) at 24-weeks post-treatment. We will report the incremental cost of rTMS per incremental remission, which will provide a standardized measure of the cost-effectiveness of rTMS therapy relative to that of “usual outpatient care”. These estimates will allow us to test a third hypothesis:

3. Relative to usual care, rTMS therapy for treatment-resistant depression is cost-effective in producing a sustained remission from acute depressive symptoms, in outpatients.

We will calculate a 95% confidence region for all estimated cost-effectiveness ratios. The ratios will be discussed in light of the cost-effectiveness of antidepressant medication and ECT. Estimates for these alternative therapies are available from published studies.^{3, 4}

C. Background

1. Prevalence

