We will estimate the average cost differences between active-rTMS and usual care during the acute treatment phase and the follow-up phase. Two analyses will be conducted, one for the period extending 24-weeks post-treatment and one for the period extending 6- to 12-months post-treatment. Total average direct and indirect health care costs for all inpatient and outpatient care will be included in our estimates. Will also produce separate estimates by study phase (treatment or follow-up), in order to isolate any post-treatment cost-offset effects. We will

collect utilization and cost data from HERC, DSS Pharmacy, PBM, and National Patient Care Database (OPC and PTF) files for at least a 30-month period, starting one year prior to the date of randomization and extending one year after the end of the treatment follow-up phase. For patients randomized to sham-rTMS, we will assume that health care utilization and costs during the post-treatment phase are representative of usual health care utilization and costs for these patients. An imputation approach (described in the next paragraph) will be used to estimate their cost of usual care during the acute treatment phase.

Usual Care Costs for Patients Randomized to Sham rTMS. As noted earlier, usual daily cost values will be imputed for patients in the comparison group. Imputation is necessary because our cost analysis requires an estimate of the difference between the cost of providing rTMS intervention and the cost of providing “usual services over a similar period of potential intervention time”. This “incremental cost” cannot be estimated by the difference in average health care costs during the acute treatment phase between the active- and sham-rTMS treatment groups. The estimator for the average incremental cost of rTMS can be expressed as $E(C | T_a) - E(C | T_u)$, where C is health care cost, T_a indicates receipt of active rTMS and T_u indicates receipt of usual care. In randomized trials, estimates of the second component of this expression, $E(C | T_u)$, are normally calculated as the average cost of care in the comparison group. In this trial that approach is problematic, because this trial will not include a “usual care” group, and the sham-rTMS group will potentially get protocol-driven additional days of care as compared to the active-rTMS group, if the latter is more effective.

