The remission outcomes data – where a sustained remission is defined as HRSD \leq 10 at 6-weeks post-treatment – will be used in conjunction with incremental treatment cost estimates to determine an incremental cost-effectiveness ratio (ICER) for the intervention. The resulting ICER will represent the estimated incremental cost per sustained remission, measured at 6-weeks post-treatment. The ratio will be expressed as: $ICER = [E(C | T_a) - E(C | T_u)] / [P(R | T_a) - P(R | T_u)]$, the difference in average acute treatment costs divided by the difference in probability of remission (R) between the two groups. Note that this assumes that the P(R) among patients receiving sham-rTMS is approximately equal to the probability of remission among usual care patients. A 95% confidence region surrounding cost-effectiveness ratios will be estimated using bootstrapping methods.¹⁷⁻¹⁹

The cost-effectiveness analysis could produce one of three major results: (1) rTMS may be cost neutral or less expensive and also more effective than usual depression care, indicating that its implementation is highly desirable; (2) rTMS might not be shown clinically effective in the VA, in which case its relative cost impact is irrelevant to VA decision-makers; (3) rTMS therapy will be more expensive than sham but will yield a greater likelihood of sustained remission. In this last case, the costs of a sustained remission will be compared with the cost of the main alternative treatment option, namely ECT. Estimates of ECT costs will be derived from the literature and from VA administrative sources.⁴

5. Sensitivity Analyses

We will test the sensitivity of our results to a number of assumptions. At a minimum, we expect them to include:

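### Appendix M sets sustained remission and the short-term cost horizon at both 6 and 24 weeks post-treatment, and no HRSD is scheduled at 6 weeks for the ICER

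*Protocol*

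**What the plan says.** **Statements at 24 weeks.** The Overview of Appendix M gives the short and long horizons as "24-weeks post-treatment, and 4- to 12-months post-treatment, respectively". Section B (Objectives) introduces its hypotheses with: "Two hypotheses about the short-term (24-weeks post-treatment) and longer term (6- to 12-months post-treatment) cost consequences of rTMS therapy will therefore be tested". It then explains the choice: "The short-term 24-week period was chosen to coincide with the collection of clinical endpoints at the end of the CSP 556 follow-up phase". It completes the definition of sustained remission (HRSD of 10 or less) for the cost-effectiveness analysis with "10) at 24-weeks post-treatment. We will report the incremental cost of rTMS per incremental remission". Section D.3 plans two cost comparisons, one to 24 weeks and one to 6 to 12 months; it has no 6-week comparison.

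**Statements at 6 weeks.** Hypothesis 1, listed directly after the sentence that announces 24 weeks, states that costs with rTMS "will be less than total costs associated with usual care at 6-weeks post-treatment". Section D.4 uses 6 weeks twice: once to define sustained remission, and once for the ratio itself: "The resulting ICER will represent the estimated incremental cost per sustained remission, measured at 6-weeks post-treatment".

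**When the HRSD is collected.** Form 20 (HRSD and MADRS) lists "Follow-up Phase Weeks: 4 8 12 16 20 24". Appendix K, section 6, starts the 24-week follow-up when acute treatment ends and places a 3-week taper, for remitters only, at the start of that follow-up. Appendix M takes health outcomes from patient interviews.

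**The concern.** Sustained remission is the only effectiveness outcome in the economic analysis. It forms the denominator of the ICER and underlies the third hypothesis, that rTMS is cost-effective. Appendix M defines it at two times, and one of them has no scheduled measurement. The two times also mean different things clinically: week 6 is 3 weeks after a remitter's last taper week (6 − 3), and week 24 is 21 weeks after it (24 − 3).

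Hypothesis 1 has a similar split: the sentence announcing it and the hypothesis itself disagree on the horizon. That matters because the Objectives expect savings to build up over time, so a shorter window is not a neutral substitute.

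The long horizon has a smaller slip. The Overview starts it at 4 months; the Objectives and D.3 start it at 6.

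**Working it through.** There is no sample-size or power figure to reproduce; Appendix M, D.6 presents none. The check compares the stated times with each other and with the visit schedule.

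**1. Count of statements.**
- 24 weeks, five times: the Overview; the Objectives three times (sentence introducing the hypotheses, rationale, remission definition); D.3.
- 6 weeks, three times: Hypothesis 1; D.4 twice.

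**2. Is there an HRSD at the stated time?** Follow-up visits on Form 20: {4, 8, 12, 16, 20, 24}.

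*Counted from the end of the acute phase:*
- Target 6: not in the set. Nearest visits 4 and 8; gap |6 − 4| = |8 − 6| = 2 weeks.
- Target 24: in the set; gap 0.

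*Counted from the end of the 3-week taper (remitters only), subtracting 3:* {1, 5, 9, 13, 17, 21}.
- Target 6: not in the set. Nearest visit 5; gap 1 week.
- Target 24: not in the set. Last visit 21; gap 3 weeks.

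Neither anchor gives a scheduled HRSD at 6 weeks. Only counting from the end of the acute phase puts 24 weeks on a visit, so the anchor needs stating along with the time.

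**3. What this does to the ICER.** D.4 divides the between-arm difference in mean acute-phase cost by the between-arm difference in the probability of remission. Both probabilities need an HRSD at the stated time. Administrative files do not hold it, and D.4 gives no rule for substituting or interpolating a neighbouring visit. As worded, the denominator has no scheduled data.

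**4. What this does to Hypothesis 1.** It compares total VA costs, built from administrative files and study cost records. No HRSD is needed, and the comparison could be made at 6 weeks. The effect is on the window: 24 − 6 = 18 weeks left out, and 18/24 = 75%.

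**5. Long horizon.** 24 weeks is 24 × 7 / 30.4375 = 5.5 months. A long-term window starting at 4 months would begin before the short-term one ends; a window starting at 6 months would not.

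**The case against.** The strongest reply is that this is leftover wording with an obvious answer. Twenty-four weeks appears more often, carries a written rationale and falls on a scheduled visit; weeks 4 and 8 are never proposed for this outcome. An analyst reading the whole appendix would probably choose 24. That stands as a reason why the correction is easy. It does not remove the fault, because D.4 is the operative definition of the ratio and says 6 weeks in both sentences.

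Four stronger readings are tempting and are not supported:

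- **That Hypothesis 1 cannot be tested as written.** It can, because it rests on cost data. Only the ICER lacks its measurement.
- **That the discrepancy has a dollar value.** A reader might scale the excess of more than $5,800 a year in section C.2 to the missing weeks (5,800 × 18/52 ≈ 2,008). That figure compares treatment-resistant with other patients, so using it as a saving assumes remission removes the whole excess; section C.2 says these relationships have not been established. It also has no bearing on the ICER, whose numerator is acute-phase cost.
- **That the long horizon should be fixed at 12 months.** D.3 does plan extraction "starting one year prior to the date of randomization and extending one year after the end of the treatment follow-up phase". But the Objectives explain that data lags and recruitment timing make the available length uncertain, and they choose the longest period within 6 to 12 months that keeps the largest sample. That rule depends on data availability, not on results. A fixed 12 months could cost late-recruited participants, so the choice is a trade-off and not an error.
- **That the trial's main conclusions are at risk.** Nothing in the text links these sentences to the clinical endpoint, safety analyses or visits.

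**Conclusion.** The contradiction is real and should be corrected. As worded, the ICER in D.4 cannot be estimated from scheduled data: the closest HRSD visits are two weeks away when counted from the end of the acute phase, and no rule covers the gap. Hypothesis 1 contradicts the sentence that introduces it, and its 6-week window omits 18 of the 24 weeks of the stated short-term period. The 4-month start in the Overview is a minor slip of the same kind.

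The conclusion rests on two assumptions. One is that Form 20 gives the full HRSD follow-up schedule; the main body of the protocol was not available for this check. The other is that post-treatment time runs from the end of the acute phase, which Appendix M does not say. The finding of no 6-week HRSD also holds if time is counted from the end of the taper. The scope is the economic analysis only.

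**What to change.** In Appendix M:

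1. Replace 6 weeks with 24 weeks in Hypothesis 1 (section B) and in both sentences of D.4.
2. State once that post-treatment time is counted from the end of the acute treatment phase, so that sustained remission is read at the week-24 HRSD visit.
3. Change the Overview's 4 to 12 months to the 6 to 12 months used in the Objectives and D.3, and keep the availability-based rule in the Objectives for the length of that horizon.

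The first change leaves the D.4 numerator at acute-phase cost, set against remission at 24 weeks. The authors should confirm that this pairing is intended.

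The cost is a few words in one appendix, with no new visits, data or participants.

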 - Patient should be routinely queried at each visit as to whether they have experienced any adverse events. Reports of significant, possible related adverse events such as changes in hearing or vision should prompt adverse event reporting and further evaluation to ensure that no patient is placed at excessive risk.

5. *Interruptions*

Every attempt shall be made to complete each treatment session as per the protocol. Interruptions during the treatment are allowed as needed for patient comfort or convenience by using the “pause” selection on the device. However, in the event that an incomplete treatment is given, this information will be recorded. Total number of treatments will be recorded. Since this is an “intent to treat” design, patients that miss treatments are not removed from the study. However, post-hoc analyses will examine the effects of compliance on overall outcome.

6. *Evaluations*

Patients are first tested for “remission” after the first 20 sessions of treatment and then again at the 25th and 30th sessions. Remission is defined as a decrease in Hamilton Rating Scale for Depression *to 10 or less*. If a patient enters “remission” after 20 sessions, then they enter a 24-week follow-up period. If a patient does not enter “remission” at the end of 20 sessions, they are offered an additional 5 sessions of treatment and retested for “remission.” This procedure may continue for a

maximum of 10 additional sessions resulting in a total of 30 sessions. Patients who do not show a treatment response at the end of 30 sessions of treatment or who drop out during treatment will be considered a treatment “failure”.

At the end of the acute treatment phase, all patients will be entered into a 24 week follow-up phase. Participants who remit will receive a 3 week treatment taper at the beginning of the follow-up phase. The taper will include 3 treatment sessions in the first week, 2 in the second week and 1 in the last week of the taper.

7. *Sham (Control) rTMS Treatment*

Sham (Control) treatment will be accomplished by using the Cool-B65-A/P coil that functions both as an active (A) and placebo (P) coil. It has a symmetrical mechanical design and no labeling on the coil indicates the active or placebo side. Consequently it is not possible for the operator to see or hear which side is used.

8. *Masking*

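### The ICER in Appendix M counts acute-phase cost only but credits remission 6 or 24 weeks later, which contradicts the appendix's own Overview

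*Protocol*

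**What the plan says.** Appendix M, D.4 writes the ICER as expected cost under active rTMS minus expected cost under usual care, over the difference in remission probability, and glosses it as "the difference in average acute treatment costs divided by the difference in probability of remission". The result is described as the "incremental cost per sustained remission, measured at 6-weeks post-treatment".

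The rest of the protocol does not fit this definition:

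- **Time of remission.** B. Objectives places the sustained remission "at 24-weeks post-treatment. We will report the incremental cost of rTMS per incremental remission". It explains the choice: "The short-term 24-week period was chosen to coincide with the collection of clinical endpoints at the end of the CSP 556 follow-up phase".
- **Cost period.** A. Overview says: "The cost-effectiveness analysis will calculate the average incremental treatment cost per incremental depression remission for these same participants and time period". The period it refers back to is the one-year period of the cost-consequences analysis. The Overview also builds the usual-care cost by adding the imputed acute-phase cost to actual follow-up costs.
- **Taper.** Appendix K, section 6: "Participants who remit will receive a 3 week treatment taper at the beginning of the follow-up phase". It amounts to six sessions, given as three, two and one over successive weeks.
- **Where savings are expected.** B. Objectives expects higher costs in the acute phase and says that "these extra costs could be partially or completely offset by savings from reduced likelihood of later hospitalization", among other sources, with the offsets building up over time.
- **Where follow-up costs are analysed.** D.3 compares total costs to 24 weeks and to 6–12 months after treatment, with separate estimates by phase.

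**The concern.** A ratio meant to price a sustained remission should count cost up to the moment at which that remission is established. D.4 closes the cost window at the end of acute treatment and then waits 6 or 24 weeks before counting the effect. Cost falling in between is absent from the numerator: ordinary VA care, any savings and, on the more natural reading, the taper.

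Two things are at stake. Analysts following D.4 and the Overview respectively would report different ICERs from the same data. And the first outcome that D.4 envisages, rTMS being no dearer and more effective, depends by the plan's own reasoning largely on later savings, which the D.4 numerator excludes. The same figure is to be set beside the cost of ECT.

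**Working it through.** The protocol gives no numerical ICER and expressly no power calculation for the economic part, so there is no figure to reproduce. The check covers what the numerator contains and how large the gap is.

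**1. Does acute exclude the taper?** Inputs: 20 to 30 sessions in blocks of 5, each block normally one week and at most 12 calendar days (Appendix K, section 3); acute phase of 4 to 11 weeks (Appendix M, A).
- Shortest: 4 blocks × 1 week = 4 weeks.
- Longest: 6 blocks × 12 days = 72 days = 10.3 weeks, i.e. in the 11th week.
- With the 3-week taper: 7 to 13.3 weeks.

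The stated 4 to 11 weeks fits the acute sessions alone. Follow-up weeks 1–3, where the taper lies, come before both candidate remission times if these are counted from the end of acute treatment.

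**2. Share of time without cost.** Formula: h / (h + a), with h the weeks from end of acute treatment to the remission rating and a the acute weeks.

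| h | a = 4 | a = 11 |
|---|---|---|
| 6 | 6/10 = 60% | 6/17 = 35% |
| 24 | 24/28 = 86% | 24/35 = 69% |

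**3. Size of the taper.** 3 + 2 + 1 = 6 sessions per remitter, that is 6/30 = 20% to 6/20 = 30% on top of that remitter's acute sessions. The numerator is a mean per patient, and Table 1 charges rTMS resources to the active arm only, so the omission is 6 × p(active) sessions per active patient.
- Illustration at 9% active and 6% sham remission (the meta-analysis of treatment-resistant depression in Appendix G, not a design assumption): 6 × 0.09 = 0.54 sessions per active patient, or 0.54/0.03 = 18 per incremental remission. Acute sessions per incremental remission are 20/0.03 = 667 to 30/0.03 = 1,000. The taper adds 1.8% to 2.7%.
- Illustration at an assumed 40% active remission, with 20 sessions for remitters and 30 for others: 6 × 0.4 = 2.4 against 0.4 × 20 + 0.6 × 30 = 26, about 9%.

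**4. Size of the omitted follow-up cost difference.** Shift in ICER = follow-up cost difference per patient / difference in remission probability. The protocol gives no follow-up difference. Assume a saving of 10–20% of 5,535 dollars per year (the FY02 VA figure per depression patient, Appendix M, C.2):
- Over 24 weeks: 5,535 × 24/52 = 2,555; saving 255 to 511 dollars.
- Over 6 weeks: 5,535 × 6/52 = 639; saving 64 to 128 dollars.

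| Remission difference | ICER shift, 24 weeks | ICER shift, 6 weeks |
|---|---|---|
| 3 points | 8,515 to 17,031 | 2,129 to 4,258 |
| 10 points | 2,555 to 5,109 | 639 to 1,277 |
| 20 points | 1,277 to 2,555 | 319 to 639 |

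A follow-up cost increase of the same size moves the ratio up by as much.

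**The case against.** The case for leaving D.4 alone has four parts.

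- **Offsets are handled elsewhere.** The sentence on savings introduces the cost-consequences hypotheses, and D.3 reports follow-up costs by phase. This stands. A reader might infer that follow-up costs are lost to the study; they are lost only to the ratio.
- **The taper may be included.** D.2 aggregates component services without an acute-only limit, Table 1 lists staff time for rTMS sessions and for services after treatment, and D.3 counts duration between the first and final day of rTMS. This stands as an ambiguity. Appendix K and the 4-to-11-week phase point the other way, so exclusion is the likelier reading but not a stated fact.
- **Acute cost per remission is a legitimate quantity.** It is narrow but interpretable, so the documents do not support saying that the ratio is meaningless or that Hypothesis 3 cannot be examined. It is, however, not what the Overview promises.
- **The percentages sound worse than they are.** A reader might take 69–86%, or the 20–30% extra sessions, as the share of cost missing. Neither is: the former is calendar time on the longer horizon, the latter applies per remitter, and the costly sessions are concentrated in the acute phase.

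Nor do the documents support a claim of bias in one direction. Omitting the taper understates the cost of rTMS; omitting follow-up savings overstates the ICER.

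**Conclusion.** Wrong as written, moderate severity, confined to the economic analysis. D.4 pairs an acute-only cost with a remission measured 6 weeks later (24 weeks by the Objectives) and contradicts the Overview on both the period and the inclusion of follow-up costs. Between 35% and 60% of the time to a 6-week endpoint, or 69% to 86% to a 24-week endpoint, is uncosted in the ratio. In the illustrations the taper is a small part of mean cost; the follow-up cost difference may matter more, above all when the remission difference is small. Those money figures rest on assumed saving and remission rates and show scale only. The net direction of error cannot be determined from the protocol. The conclusion rests on Appendices K and M as they stand. Clinical endpoints are not affected.

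**What to change.** State one remission time point and one cost window, running from randomisation to that time point, and use them in Appendix M, A, B, D.3 and D.4; the 6-week, 24-week and one-year statements must be reconciled. A practical consideration: the HRSD form (Form 20) lists follow-up ratings at weeks 4, 8, 12, 16, 20 and 24, so week 24 has a scheduled rating and week 6 does not.

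Within the window:

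- **Active rTMS:** acute, taper and follow-up VA costs, with taper sessions costed as intervention.
- **Usual care:** the imputed acute-phase cost of D.3 plus the sham arm's actual follow-up costs, without sham taper sessions or other visits that exist only because of the sham protocol. A plain comparison of observed costs by arm from randomisation is not a substitute, because D.3 explains why sham acute-phase costs do not represent usual care.
- **Duration used in the imputation:** say that it ends with the last acute session. If it ran to the last taper session, those weeks would be counted in usual care both by imputation and as follow-up.
- **Component:** report the acute-only cost difference alongside the full ratio.

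The cost is wording in several places of Appendix M, not in D.4 alone. No new data are needed: D.3 already plans at least 30 months of cost data per patient, to one year beyond follow-up.
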